2.1.1.7 Time unit

A year length is defined as 365.25 days. A month length is 30.4375 days (365.25/12). Duration reported in months will be obtained by dividing duration in days by 30.4375. Duration reported in years will be obtained by dividing duration in days by 365.25.

2.1.1.8 Baseline

For efficacy evaluations, the last non-missing assessment, including unscheduled assessments on or before the date of randomization is taken as “baseline” value or “baseline” assessment. In the context of baseline definition, the efficacy evaluations also include PRO.

For safety evaluations (e.g., laboratory assessments, ECGs, and vital signs), the last available assessment, including unscheduled assessments, on or before the start of study treatment as described in [Section 2.1.1.4](#) will be used as the “baseline” assessment. Assessments specified to be collected post-dose on the 1st date of treatment are not considered as baseline values.

If participants have no value as defined above, the baseline results will be considered missing.

Since study treatment in the randomized treatment phase can still potentially contribute to the safety profile in the cross-over and re-treatment phase, therefore, for cross-over and re-treatment analyses, baseline for safety analysis is the same as defined above, i.e., last available assessment on or before the start of study treatment.

For efficacy evaluations of the cross-over and re-treatment period, the last available assessment on or before first cross over treatment/re-treatment with Lutathera® is regarded as “baseline” for the assessments.

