3.1 Screening Phase

The screening phase should be shortened as much as possible, in order to treat the patients possibly within 2 weeks after the consent signature.

The randomization should be performed as soon as possible, after all eligibility criteria are verified. Patients under octreotide long-acting before study entry should have their last dose carefully programmed during the screening phase (in case of randomization in the Lutathera arm a washout period of 6 weeks from octreotide long-acting must be observed prior to Lutathera injection).

As Lutathera production and shipment will take circa 12 days to be arranged, if a patient is randomized in the Lutathera arm, Lutathera first dose should be ordered within 24h after randomization.

The baseline CT/MRI scan should be taken possibly on the same day as randomization or immediately before (within 1 week) to ensure that it reflects the disease status closely before the therapy start.

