8.4 Quality of Life

The impact of treatment on health related QoL will be assessed using the EORTC QLQ-G.I.NET21, EORTC QLQ-C30 and EQ-5D-L5 questionnaires, which will be filled in by the patient prior to know CT scan/MRI result. Changes from baseline will be assessed every 12 ± 1 week from the first treatment date until the end of treatment.

Forms in Country-specific languages will be provided by the Sponsor.

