Octreotide long- acting 30 mg	Injectio Last in	ons t jecti	o b on :	e ao sho	dmir uld	niste be a	ered adm	at le inist	eas ere	t aft d at	er 4 Iea	hou st 6	rs a wee	fter ks l	eac befc	ch L ore (uta eac	the h L	ra ti utat	reat ther	tme ra in	nt c nfus	or tl sior	he o	day	after (pret	ferred op	tion),	-		
Octreotide SC	Octreo	tide	S.C.	. inj	ectio	on c	can b	be g	iver	n as	nee	ded	but	mu	st b	e si	topp	bed	24	n be	etor	e e	each	ו Lu	utati	nera infusi	on				
QoL(QLQ-G.I.NET21, QLQ-C30, EQ-5D-5L)	X	X				2	X					X			X			Х			X	<			Х		Х	X			Х
Survival information	Х	Х	X		$\langle \rangle$	$\langle \rangle$	x >	$\langle \rangle$	< 🗆	X 🛛	X	x)	$\langle \rangle$	()	X	Х	Х	Х	Х	Х	X	$\langle \rangle$	Х	Х	Х	Х	Х	Х		Х	Х

-TREATMENT PHASE:

- TREATMENT: Lutathera; 4 administrations at 8±1-week intervals
- TREATMENT: 30 mg octreotide long-acting injections to be administered the day after each Lutathera infusion Due to the 6 weeks washout prior to each Lutathera injection, octreotide long-acting 30 mg is administered every 8 weeks during Lutathera treatment (including during the optional treatment extension phase) and every 4 weeks after last Lutathera treatment. IF REQUIRED, RESCUE TREATMENTS: Octreotide s.c. injections (to be stopped 24 h before each Lutathera infusion)
- 1- Before the PFS primary analysis (i.e. 99 evaluable and centrally confirmed disease progressions or death events), patients continue the Treatment Phase until progression. After the PFS primary analysis, the Treatment Phase duration becomes fixed (72 weeks).
- 2- Via echocardiography, only in patients with history of congestive heart failure (patients with uncontrolled congestive heart failure (NYHA II, III, IV) aren't eligible according to exclusion criteria)
- 3- Randomization must be performed once all screening assessments are complete. The screening phase must be shortened as much as possible in order to treat the patients possibly within 2 weeks from the consent date. As Lutathera production and shipment will take approximately 12 days to be arranged, if a patient is randomized in the Lutathera arm, Lutathera first dose must be ordered immediately after randomization. The baseline CT/MRI scan should be taken possibly on the same day of randomization or immediately before (within 1 week) to ensure that it reflects the disease status closely before the therapy start.
- 4- Additional pregnancy tests for Germany only. The pregnancy test at EoT is for Germany and UK.

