2.1.1.11 Windows for multiple assessments

For the definition of time windows for visits please refer to the study protocol, [[Tables 8-3](#)] and [[Table 8-4](#)]. Variations of ± 1 week in the visits schedule are allowed.

Time windows will be defined for descriptive summary of PRO data by visit and longitudinal data analysis. If more than one assessment is available in the same time window, the assessment closest to the planned date will be considered. If two assessments are obtained equidistant compared to the scheduled visit day, the assessment obtained prior to visit will be considered.

Table 2.1-1 Time Window for PROs

Time Window	Planned Visit Timing	Time Window Definition
On treatment		
Baseline	On or before Study Day 1*	\leq Study Day 1*
Week 12	Study Day 78	Study Days 2 – 120
Week 24	Study Day 162	Study Days 121 – 204
Week 36	Study Day 246	Study Days 205 – 288
Every 12 weeks thereafter		
Week 12^*k ($k = 4, 5, \dots$)	$d = 7^*(12^*k-1)+1$	Study Days $d-41$ to $d+42$ Note: window for last visit before EOT: $d-41$ to EOT date-1

End of treatment during randomized treatment period

End of treatment	N.A.	Data collected under EOT visit
* Study Day 1 = randomization date		

Data from all assessments (scheduled and unscheduled), including multiple assessments, will be listed.

Last contact date

The last contact date will be derived for patients not known to have died at the analysis cut-off using the last complete date among the following:

Table 2.1-2 Last contact date data sources

Source data	Conditions
Date of Randomization	No Condition
Last contact date/last date patient was known to be alive from Visit Form 3	Patient status is reported to be alive
Start/End* dates from drug administration record	Non-missing dose. Doses of 0 are allowed.
End of treatment date from end of treatment page	No condition.
Date of PRO assessment	At least one non-missing answer to questionnaire
Tumor (RECIST) assessment date	For non-target lesion: non-missing lesion status; For target lesion: non-missing lesion diameter; For new lesion: "Is there a new lesion?" = yes
Laboratory/PK collection date	Sample collection marked as 'done'.
Vital signs and ECG date	At least one non-missing parameter value
Performance Status date	Non-missing performance status
Start/End dates of AE	Non-missing verbatim term
Concomitant medication/Non-drug therapy date	Non-missing medication
Physical exams	At least one non-missing value

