For the symptom scales (SS), the single items and Global health status /QoL the score is calculated by the formula:

$$\text{Score} = \{(RS - 1) / \text{range}\} \times 100,$$

For a single item, RS is identical to the score of the item itself.

The “range” value is the difference between the maximum possible value of RS and the minimum possible value for RS. The range = 3 for all scales and single items except for “Global health status /QoL”. For “Global health status /QoL” the range is 6.

The formulas for the scores are linear transformations of 0-100.

Time to deterioration (TTD) is the main analysis and is defined as time from randomization to the first deterioration of at least 10 points in domain score compared to the baseline score for the same domain or death while on treatment (Strosberg *et al.* 2018). Patients with no deterioration are censored at the last QoL assessment date. Patients with no baseline and/or no follow-up are censored at randomization.

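### A Week 0 QoL form dated after randomization counts as post-baseline, and no rule stops it from being a time-to-deterioration event

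*SAP*

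**What the plan says.** - **Baseline.** SAP 2.1.1.8: "For efficacy evaluations, the last non-missing assessment, including unscheduled assessments on or before the date of randomization is taken as" baseline, and "In the context of baseline definition, the efficacy evaluations also include PRO". The safety baseline in the same section runs to the start of study treatment instead, with its own guard: "Assessments specified to be collected post-dose on the 1st date of treatment are not considered as baseline values". The QoL baseline has no comparable guard.
- **Forms collected.** In Protocol Tables 8-3 and 8-4 (section 8.5.10), the row labelled "QoL(QLQ-G.I.NET21, QLQ-C30, EQ-5D-5L" is marked at Screening, at Week 0, and then every 12 weeks in both arms. Protocol section 8 counts visits other than tumor imaging from first treatment. Protocol 8.4 places the assessments of change every 12 ± 1 "week from the first treatment date until the end of treatment".
- **Gap between randomization and first dose.** Protocol 3.1: "As Lutathera production and shipment will take circa 12 days to be arranged". The same section requires a 6-week washout from long-acting octreotide before the first Lutathera dose. It applies only to patients already on that drug and only in the Lutathera arm.
- **Endpoint.** SAP 2.6.1: "Time to deterioration (TTD) is the main analysis and is defined as time from randomization to the first deterioration of at least 10 points" against baseline, or death on treatment. SAP 2.6.3 uses assessments collected on randomized treatment and expressly drops only those after its end. Table 2.6-2 has no rule for a form completed before, or on the day of, first dose.
- **Use.** TTD in global health, diarrhea, fatigue and pain fills the last four steps of the confirmatory hierarchy (SAP 2.6.1, 5.4.1). SAP 3.1 states that no power was calculated for them.

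**The concern.** A patient whose first dose falls on a later date than randomization completes one more QoL form that is compared with baseline before any treatment effect is possible. Worsening on it would reflect ordinary score fluctuation, reaction to a known allocation in an open-label trial, or, for some Lutathera patients, interruption of long-acting octreotide. TTD is a first-event endpoint with no confirmation and no minimum time, so one such form settles the patient's outcome.

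The supply lag and the washout belong to the Lutathera arm, so the extra form may occur there more often. The hierarchy is also strictly ordered: a test lost at global health blocks diarrhea, fatigue and pain.

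**Working it through.** **1. The plan's own figures.** There is no TTD power figure to reproduce. The planned days in SAP Table 2.1-1 follow from d = 7 × (12k − 1) + 1: k = 1, 2, 3 gives Days 78, 162, 246, as tabulated. Day 1 is the randomization date.

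**2. Where the Week 0 form falls.** A form completed on the day of first dose, L days after randomization, has Study Day L + 1. The Week 12 form has Study Day L + 84 + 1.

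| L (days) | Week 0 form | Status under 2.1.1.8 | Week 12 form |
|---|---|---|---|
| 0 | Day 1 | baseline | Day 85 |
| 1 | Day 2 | post-baseline | Day 86 |
| 12 | Day 13 | post-baseline | Day 97 |
| 42 | Day 43 | post-baseline | Day 127 |

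With the protocol's 12-day lag, the earliest scheduled form that can give an event is at Day 13. If the Week 0 form is barred, it is at Day 97.

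**3. Whether another rule removes it.** SAP 2.1.1.10 opens the randomized treatment period on the date of first dose, so a form dated that day is on-treatment. A form dated between randomization and the dosing day lies in the pre-treatment period of 2.1.1.10 but inside the randomized treatment phase of 2.1.1.9. SAP 2.6.3 does not say which of the two governs. Neither 2.6.1 nor Table 2.6-2 settles it, and no TTD analysis in 2.6.5 or 2.6.6 drops the form.

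**4. How small a change is an event.** From the scoring formula in SAP 2.6.1, one step on a scale is 100 / (items × range).
- Diarrhea: 100 / (1 × 3) = 33.3, so one category is enough.
- Pain: 100 / (2 × 3) = 16.7, one step.
- Fatigue: 100 / (3 × 3) = 11.1, one step.
- Global health: 100 / (2 × 6) = 8.3, so two steps (16.7).

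**5. How often this could happen by chance.** The documents give no rate. As an assumption, take a score SD of 20 to 30, test-retest reliability r of 0.7 to 0.9, and a normal approximation. Then P = 1 − Φ(10 / (SD × √(2(1 − r)))). At SD 20 and r 0.9 the SD of the difference is 8.9 and P = 13%. At SD 30 and r 0.7 it is 23.2 and P = 33%.

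**6. Effect on the test.** Simulations used 148:74 patients, 12-weekly forms and a one-sided 2.5% log-rank test. All deterioration rates are assumed.

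*Scenario A* (15% deterioration per control form, treatment ending at the design PFS medians), with 5, 10, 20% worsening at Week 0:

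| | 5% | 10% | 20% |
|---|---|---|---|
| Power, per-form HR 0.55 (82% without the form), both arms affected | 74% | 66% | 54% |
| Same, Lutathera only | 56% | 30% | 3% |
| Apparent HR at true HR 1, Lutathera only | 1.10 | 1.21 | 1.44 |

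A smaller run of a similar model (800 trials per case) gave 1.10, 1.19 and 1.42 for the last row. With half the control patients also having a later Week 0 form it gave 1.06, 1.10 and 1.17. With 80% of them it gave 1.02, 1.03 and 1.06.

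*Scenario B* (control median TTD 12 months, true HR 0.6, power 66% without the form), with 10, 20, 30% worsening: power is 54, 41, 31% if both arms are affected, and 19, 2, 0% if only Lutathera is. At true HR 1, the chance of a false claim for Lutathera stays between 2.4% and 2.8% when both arms are equally affected. It is 0.2% or less when only Lutathera is.

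**The case against.** The best defence is that the estimand counts time from randomization in all randomized patients, so worsening while waiting for the drug is a legitimate outcome. Protocol 8.4 also shows that Week 12 from first treatment was meant as the first comparison, which would make this a drafting gap. The first part has some force, and it is why the time origin should stay and the analysis with Week 0 forms should still be reported. The second supports the fix, because the SAP contains no rule that carries out that intention.

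Several stronger readings are tempting, and the documents do not support them.
- A reader might infer from "Study Days 2 – 120", the Week 12 row under the on-treatment heading of Table 2.1-1, that the SAP classes the form as on-treatment for TTD. SAP 2.1.1.11 limits those windows to by-visit summaries and longitudinal analysis. Within a window the form nearest the planned day is used, so a Week 0 form enters only if none is nearer.
- Nor does Day 2 override the general window formula. That formula is given only from k = 4, and Week 12 has its own row.
- It is an inference that the form is completed before dosing. The schedules give no clock time, and the SAP works by date.
- The one-arm figures would need every control patient to be dosed on the day of randomization. No passage says so.

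**Conclusion.** The point holds as a should-fix and a cheap improvement. When first dose falls on a later date than randomization, which is the norm in the Lutathera arm, the Week 0 form is post-baseline, and a worsening of 10 points on it can be a TTD event. That is clear for a form dated on the dosing day and unresolved for one dated earlier.

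The direction does not rest on assumed rates: dilution if both arms are alike, bias against Lutathera if its Week 0 forms fall after randomization more often. A reader might fear a false claim of QoL benefit, but neither pattern inflates type I error in Lutathera's favour. PFS, ORR and the 99-event calculation are untouched.

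The size is not known. Every power and hazard-ratio figure rests on assumed deterioration rates. The figures with only Lutathera affected are a worst-case bound, and they shrink towards no bias as more control patients are also dosed after randomization.

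**What to change.** 1. In SAP 2.6.1 and 2.6.3, keep the 2.1.1.8 baseline and the randomization time origin. State that QoL forms dated on or before the date of first study treatment are not post-baseline assessments for TTD, so the event search starts with the first form after that date.
2. Censor at randomization, as in Table 2.6-2 situation A, randomized patients who are never dosed or have no form after first dose. Deaths stay as in 2.6.1.
3. For by-visit summaries and MMRM, bar the same Week 0 form from filling the Week 12 window. Leave the PRO clock and the window bounds unchanged.
4. Report the TTD analysis that includes Week 0 forms as a supplementary analysis.

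The cost is a few sentences, a date filter and one extra output, with no new data. The small downside is that genuine worsening between randomization and first dose is not counted in the main TTD analysis; item 4 keeps it visible.

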12.5.3 Safety endpoints

For all safety analyses, the safety set will be used. All listings and tables will be presented by treatment group.

The frequency of adverse events and laboratory toxicities (scored according to CTCAE 5.0 grade or current version) will be presented.

All adverse events (AEs), whether or not spontaneously reported by the patient, will be recorded starting from the signing of the ICF until the end of the Treatment Phase.

Safety summaries (tables, figures) include only data from the on-treatment period with the exception of baseline data which will also be summarized where appropriate (e.g. change from baseline summaries). In addition, a separate summary for death including on treatment and post treatment deaths will be provided. In particular, summary tables for adverse events (AEs) will summarize only on-treatment events, with a start date during the on-treatment period (*treatment-emergent* AEs).

The on-treatment period lasts from the date of first administration of study treatment to 30 days after the date of the last actual administration of any study treatment.

The overall observation period will be divided into three mutually exclusive segments:

- pre-treatment period: from day of subject's informed consent to the day before first dose of study medication
- on-treatment period: from day of first dose of study medication to 30 days after last dose of study medication
- post-treatment period: starting at day 30+1 after last dose of study medication.
- There will be a dedicated presentation of safety for patients who cross-over.

Adverse events

All information obtained on adverse events will be displayed by treatment group and subject.

The number (and percentage) of subjects with treatment emergent adverse events (events started after the first dose of study medication or events present prior to start of double-blind treatment but increased in severity based on preferred term) will be summarized in the following ways:

- 1. by treatment, primary system organ class and preferred term.
- 2. by treatment, primary system organ class, preferred term and maximum severity.
- 3. by treatment, Standardized MedDRA Query (SMQ) and preferred term

Separate summaries will be provided for study medication related adverse events, death, serious adverse events, other significant adverse events leading to discontinuation and adverse events leading to dose adjustment.

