The number (and proportion) of subjects with AESI/related to identified and potential risks (see Section 10.1) will be summarized by treatment.

A subject with multiple adverse events within a primary system organ class is only counted once towards the total of the primary system organ class.

Vital signs

All vital signs data will be listed by treatment group, subject, and visit/time and if ranges are available, abnormalities (and relevant orthostatic changes) will be flagged. Summary statistics will be provided by treatment and visit/time.

12-lead ECG

PR, QRS, QT, QTcF, and RR intervals will be obtained from 12-lead ECGs for each subject during the study. ECG data will be read and interpreted (centrally/locally).

All ECG data will be listed by treatment group, subject and visit/time, abnormalities will be flagged. Summary statistics will be provided by treatment and visit/time.

Clinical laboratory evaluations

All laboratory data will be listed by treatment group, subject, and visit/time and if normal ranges are available abnormalities will be flagged. Summary statistics will be provided by treatment and visit/time. Shift tables using the low/normal/high/ (low and high) classification will be used to compare baseline to the worst on-treatment value.

Grading of laboratory values will be assigned programmatically as per NCI Common Terminology Criteria for Adverse Events (CTCAE) version 5.0 or current version. The calculation of CTCAE grades will be based on the observed laboratory values only, clinical assessments will not be taken into account.

CTCAE Grade 0 will be assigned for all non-missing values not graded as 1 or higher. Grade 5 will not be used.

For laboratory tests where grades are not defined by CTCAE, results will be categorized as low/normal/high based on laboratory normal ranges.

The following summaries will be generated separately for hematology, and biochemistry tests:

- 1. Listing of all laboratory data with values flagged to show the corresponding CTCAE grades if applicable and the classifications relative to the laboratory normal ranges
- 2. For laboratory tests where grades are defined by CTCAE,
- 3. Worst post-baseline CTCAE grade (regardless of the baseline status). Each subject will be counted only once for the worst grade observed post-baseline.
- 4. Shift tables using CTCAE grades to compare baseline to the worst on-treatment value
- 5. For laboratory tests where grades are not defined by CTCAE,

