12.6.4 Re-treatment with Lutathera

Safety will be presented in a similar manner to that in Section 12.5.3 for those participants who receive re-treatment with Lutathera during the re-treatment period. The re-treatment period lasts from the date of first administration of re-treatment with Lutathera to progression or death during the re-treatment period.

All information obtained on adverse events will be displayed by subject.

All vital signs data will be listed subject, and visit/time and if ranges are available, abnormalities (and relevant orthostatic changes) will be flagged. Summary statistics will be provided by visit/time.

All ECG data (as per local assessment) will be listed by subject and visit/time, abnormalities will be flagged. Summary statistics will be provided by visit/time.

All laboratory data will be listed by subject, and visit/time and if normal ranges are available abnormalities will be flagged. Summary statistics will be provided by visit/time. Shift tables using the low/normal/high/ (low and high) classification will be used to compare the latest assessment before re-treatment to the worst re-treatment value.

All efficacy analyses for ORR, DoR, PFS, PFS2, and OS will be descriptive. Definitions for ORR, DoR, and PFS (as per local assessment) are the same definitions in Section 12.5.2 except that the baseline will be based on the tumor assessment which demonstrated progression thus allowing re-treatment with Lutathera. Definitions for OS and PFS2 are the same to that in Section 12.5.2 and Section 12.6.1, respectively.

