2.8.3 Laboratory data

The laboratory assessments require that blood samples for hematology and blood chemistry, and a urine sample for urinalysis are taken (see Table 8-2, Table 8-3, and Table 8-4 of the study protocol). Laboratory assessments will be performed at the investigational site.

The following laboratory parameters will be investigated and analyzed:

- (1) Haematology: White blood cells (WBC) with differential (i.e., Lymphocytes, Monocytes, Neutrophils, Eosinophils, Basophils), Platelets, Haemoglobin (Hb), Haematocrit, MCV
- (2) Blood chemistry: Blood urea nitrogen (BUN) or Urea, Serum creatinine, Uric acid, Albumin, Total bilirubin, ALP, AST/ASAT, ALT/ALAT, Gamma-GT, Sodium, Potassium, LDH, CgA (centralized assessment), Haemoglobin A1C (GlycoHb), fT4, Calcium, Magnesium, Fasting blood glucose, Thyrotropin, Creatinine clearance (calculated by the Cockroft-Gault formula)
- (3) Pregnancy test (if applicable)

On analyzing laboratory, data from all sources (central and local laboratories) will be combined. The summaries will include all assessments available for the lab parameter collected no later than 30 days after the last study treatment administration date (see [Section 2.1.1](#)). Separate

summaries will be generated for the randomized period, cross-over period, and re-treatment period.

Laboratory values outside normal ranges will be listed and flagged. The following flags will be used:

‘+’: ‘Higher than reference value’

‘-’: ‘Lower than reference value’

The respective parameter and the flagged value will be presented patient-wise by visit together with the reference values

The following summaries will be produced for hematology and biochemistry laboratory data (by laboratory parameter and treatment):

- Worst post-baseline CTC grade (regardless of the baseline status). Each subject will be counted only for the worst grade observed post-baseline.
- Shift tables using CTC grades to compare baseline to the worst on-treatment value
- For laboratory tests where CTC grades are not defined, shift tables using the low/normal/high/(low and high) classification to compare baseline to the worst on-treatment value.
- Box plots of laboratory values by scheduled time point.

The following listings will be produced for the laboratory data:

- Listings of all laboratory data, with CTC grades and classification relative to the laboratory normal range. Lab data collected during the post-treatment period will be flagged.

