3.1 Power for analysis of key secondary variables

No power calculation has been performed for the key secondary variables.

4 Change to protocol specified analyses

Not applicable

5 Appendix

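### For re-treatment laboratory shift tables, the SAP uses the pre-study baseline where protocol 12.6.4 uses the last value before re-treatment, and SAP section 4 declares no change

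*SAP*

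**What the plan says.** Protocol 12.6.4 covers patients re-treated with Lutathera. Its laboratory shift tables, in the low/normal/high classification, "will be used to compare the latest assessment before re-treatment to the worst re-treatment value". For the rest it presents safety along the lines of protocol 12.5.3, where the graded tables are described as "Shift tables using CTCAE grades to compare baseline to the worst on-treatment value".

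SAP 2.1.1.8 sets one safety baseline for every period. It reasons: "Since study treatment in the randomized treatment phase can still potentially contribute to the safety profile in the cross-over and re-treatment phase". From this it draws its rule for both later periods: "baseline for safety analysis is the same as defined above, i.e., last available assessment on or before the start of study treatment". The same section resets the efficacy baseline at the first cross-over or re-treatment dose.

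SAP 2.8.3 lists "Shift tables using CTC grades to compare baseline to the worst on-treatment value", adds low/normal/high shift tables for tests without CTC grades, and asks for separate summaries for the randomized, cross-over and re-treatment periods.

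SAP section 4, headed "Change to protocol specified analyses", is marked not applicable. The SAP introduction states that it is based on protocol version 2.0, which contains section 12.6.4.

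**The concern.** The two documents give different reference values for the same table, and the SAP does not say that it has changed anything. One of the exploratory objectives (protocol Table 2-1, SAP Table 1.2-1) concerns laboratory toxicities arising while patients are being re-treated. A re-treated patient has already had four Lutathera doses, a further period without progression, and then progression. If the reference value predates all of that, the re-treatment shift table mixes what the first course left behind with what the second course added. A reader would naturally take a shift in that table as something that happened during re-treatment.

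**Working it through.** The plan gives no figure to reproduce here. The check is a comparison of texts, a count of how old the reference is, and an illustration with assumed laboratory values.

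**1. Reference value for re-treatment laboratory shifts**

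- Protocol 12.6.4: latest value before re-treatment, compared with the worst value in re-treatment.
- SAP 2.1.1.8 with 2.8.3: last value before the first dose of the randomized phase, compared with the worst value in the period.

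Both cannot be the reference for the same table, and SAP section 4 records no departure.

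**2. Age of the SAP reference at the first re-treatment dose**

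Protocol 5.2.2 requires four doses, then at least 6 months of disease control after the fourth, with a 2-week allowance. Doses are 8 ± 1 weeks apart, so there are three intervals. Six months is taken as 26 weeks, and a month as 30.4375 days (SAP 2.1.1.7).

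- Nominal: 3 × 8 + (26 − 2) = 48 weeks; 48 × 7 / 30.4375 = 11.0 months.
- Shortest intervals: 3 × 7 + (26 − 2) = 45 weeks; 45 × 7 / 30.4375 = 10.3 months.

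Both are minimum ages, because progression and re-treatment eligibility checks come afterwards.

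**3. What the tables would show**

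The values below are assumed. Grades follow the CTC table in SAP 5.3, with its lower normal limits (lymphocytes 1.5, platelets 150, WBC 3.9, Hb 120 for women). Units are 10⁹/L, and g/L for Hb.

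| Test | Before study | Before re-treatment | Worst in re-treatment | Grade shift, SAP reference | Grade shift, pre-re-treatment reference |
|---|---|---|---|---|---|
| Lymphocytes | 1.8 | 0.6 | 0.6 | 0→2 | 2→2 |
| Lymphocytes | 1.8 | 0.4 | 0.4 | 0→3 | 3→3 |
| Platelets | 220 | 80 | 80 | 0→1 | 1→1 |
| WBC | 6 | 2.1 | 2.1 | 0→2 | 2→2 |
| Hb | 130 | 82 | 82 | 0→2 | 2→2 |
| Lymphocytes, new fall | 1.8 | 0.9 | 0.4 | 0→3 | 1→3 |

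The first five rows have no new toxicity, yet each shows a shift under the SAP. Rows two and six are clinically different but occupy the same 0→3 cell under the SAP.

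In low/normal/high terms, row two is normal to low under the SAP and low to low under the protocol. Row six is also low to low under the protocol, so only a graded table with the later reference shows that new fall.

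**4. How much can be carried over**

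Protocol Table 8-2 requires Hb, WBC, platelets, creatinine clearance and bilirubin to meet the entry limits before each Lutathera dose. With limits of 8.0 g/dL, 2 × 10⁹/L and 75 × 10⁹/L, the carried-over grade is at most 2 for Hb, 2 for WBC and 1 for platelets. Lymphocytes have no such limit, and the footnote to protocol Table 6-4 exempts grade 3 or 4 lymphopenia from dose modification. Lymphopenia is therefore the clearest case.

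**The case against.** The SAP choice is deliberate. Its reason is stated, and its revision log for August 2023 records a clarification of the cross-over and re-treatment baseline. Counting toxicity from first exposure is a legitimate safety view. This stands as a reason to show a cumulative table. It does not explain why the table that the protocol specifies should disappear, or why section 4 is blank.

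The protocol's explicit rule is also narrow. It names the low/normal/high classification, and for graded shifts protocol 12.6.4 points back to 12.5.3, which speaks only of baseline. This stands too: the literal contradiction is in the low/normal/high shifts, and carrying the same reference to the graded shifts is the consistent reading, not a separate rule.

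A reader might infer four stronger things that the documents do not support.

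- *That cross-over safety also contradicts the protocol.* Protocol 12.5.3 says only "There will be a dedicated presentation of safety for patients who cross-over" and sets no baseline for it.
- *That toxicity grades or event rates are distorted.* SAP 5.3 derives CTC grades without reference to baseline. The worst-grade table in SAP 2.8.3 ignores baseline status. SAP 2.8.1 defines treatment-emergent events by onset or worsening in the period. Notable-ECG summaries cover the randomized period only.
- *That vital-sign and liver outputs breach the protocol.* The notable vital-sign criteria (SAP Table 2.8-3) and the combined liver categories do depend on baseline, but the protocol names no other baseline for them. Blood pressure and pulse also need an absolute threshold, and the single-parameter liver cut-offs are multiples of the upper normal limit.
- *That old and new toxicity could never be separated.* SAP 2.8.3 also provides full listings and box plots by time point, so patient-level comparison remains possible. The loss is in the summary table.

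**Conclusion.** The point holds for re-treatment laboratory shift tables. SAP 2.1.1.8 with 2.8.3 replaces the reference that protocol 12.6.4 specifies, and SAP section 4 wrongly indicates that nothing has changed. The practical effect is that a carried-over, unchanged abnormality is tabulated as a shift during re-treatment, against a reference at least about 10 to 11 months old.

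The number of patients affected cannot be derived. The documents do not say how many will carry an abnormality into re-treatment, and a share such as 10 to 30% would be an assumption with nothing in them to support it. The worked values are likewise illustrative.

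The analyses are descriptive and re-treatment is an exploratory objective. SAP 2.1.1.10 produces only selected safety output for these periods at the primary PFS analysis. Inference on PFS and the key secondary endpoints is untouched. The mismatch should be corrected because it is undeclared and bears on what the re-treatment table is meant to show.

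**What to change.** In SAP 2.1.1.8 and 2.8.3, make the last value on or before the first re-treatment dose the reference for re-treatment laboratory shift tables. Keep the pre-study baseline as a second table labelled as cumulative toxicity. If the sponsor prefers the pre-study baseline as the main reference, declare and justify that in SAP section 4.

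For cross-over, and for the baseline-dependent vital-sign and combined liver criteria, showing the period-start reference beside the pre-study one is an optional improvement, since the protocol sets no other baseline there.

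The cost is SAP wording, one more baseline flag and a duplicate set of shift tables. No new data are needed: protocol 8.5.2 already schedules laboratory tests within 2 weeks before each Lutathera dose, including in re-treatment.
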